	Screen	1	2	3	4	5	6	7	8	9	10	11	12	13	14	15	16	17	18	19	20	21	22	23	24	25	26	27	28	29	30	31	32				
ALL PATIENTS																																					
Check inclusion / exclusion criteria	X																																				
Informed consent	X																																				
Optional blood sample (check consent)	X																																				
Request stored pathology samples (check consent)	X																																				
Offer OxMdG or IrMdG	X																																				
Send sample of primary cancer for KRAS analysis	X																																				
Randomisation	X																																				
Calculate GFR (if < 50 ml/min, measure GFR)	X																																				
QoL questionnaire	X																																				
CT scan (Chest, abdo, pelvis or equiv.)	X*																																				
Tumour marker (CEA or other)	X*																																				
Liver resection surgery	X*																																				
Collect pathology samples (check consent)																																					
OxMdG and IrMdG PATIENTS																																					
Check adverse events		X																																			
Clinical evaluation		X																																			
RECIST response	X																																				
NCI CTC scores		X																																			
WHO PS		X																																			
FBC, U&Es, LFTs, magnesium**		X																																			
Chemotherapy - folinic acid		X																																			
Chemotherapy - Oxaliplatin (OxMdG) or Irinotecan (IrMdG)		X																																			
Chemotherapy - 5FU		X																																			
Chemotherapy - Cetuximab (if applic.)		X																																			
Return data to UoSCTU		X																																			

Results from FBC, U&Es, LFTs required before patient attends baseline visit; delay between baseline visit to week 1 visit must be < 3 weeks if clinically acceptable; * = procedure may be performed at screening or baseline but must be within 6 weeks prior to chemotherapy; † = if raised at baseline; ** = measure in all patients showing possible symptoms of hypomagnesaemia; QoL = quality of life; NCI CTC = national cancer institute common toxicity criteria; WHO PS = world health organisation performance status; follow-up schedule (including CT scans) described section 11 should be followed after the treatment phase

4. Introduction

Background

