- The ambulatory technique for OxMdG and IrMdG is described in AAppendix III. These regimens may also be given on an inpatient basis, but investigators are urged to use outpatient ambulatory treatment whenever possible.

9.b Treatment duration and breaks

- **Arm A (Control, OxMdG / IrMdG):** These patients will receive 12 weeks of pre-operative and 12 weeks of post-operative chemotherapy dependent on cumulative toxicity, post-surgical performance status or because of patient choice to stop chemotherapy. Patients in this arm should continue on treatment with no more than a three week interval off treatment for any reason although the post surgical interval can be 6 weeks. *The cumulative toxicity that is most likely to occur is the neuropathy associated with Oxaliplatin, which increases in incidence from about 12 weeks duration of therapy. If this occurs, patients may continue on the fluorouracil component of the regimen with dose increment as indicated in Appendix I.* If the neuropathy resolves to < grade 1 the Oxaliplatin may be reintroduced cautiously at the investigator's discretion.
- **Arm B: OxMdG / IrMdG plus Cetuximab:** These patients will receive chemotherapy as Arm A above plus Cetuximab. Patients in this arm should continue on treatment with no more than a three week interval off treatment for any reason although the post surgical interval can be 6 weeks. Cetuximab will be continued if chemotherapy is stopped because of toxicity or patient choice, but should be discontinued on recurrence or unacceptable Cetuximab toxicity. Full details of Cetuximab administration and dose reduction and delays are given in Appendix I.

9.c Surgery

The liver resection is carried out **at the earliest 4 weeks** after the last administration of chemotherapy and Cetuximab, and within 2 to 6 weeks of CT scanning at the end of the pre-operative period. Patients who progress during the first 12 weeks of chemotherapy and who are still operable should be considered for surgery. However these patients are unlikely to be salvaged with surgery and consideration should be given to second-line chemotherapy. In addition, the patient must have completely recovered from side effects, the general condition according to WHO grade must be ≤ 1 and liver function must be adequate for liver surgery.

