11.e Every chemotherapy cycle (day 1, or up to 3 working days before)

1. Clinical evaluation (doctor/nurse), to include NCI toxicity scores from previous cycle (see Appendix XI) and current WHO PS (see Appendix VII)
2. Check FBC, U&Es, and LFTs (see regimen details in Appendix I for critical values).
3. Measure and record magnesium levels.
4. Recalculate drug doses if patients' weight has changed by more than 10%, or follow local policy.
5. Record Cetuximab administration details for patients in Arm B.
6. These data should be collated on the **Treatment Form** which is returned to UoSCTU every 6 weeks (i.e. after every 3 cycles of OxMdG or IrMdG)

Patients should also complete QoL questionnaires during both pre- and post-operative chemotherapy at the beginning of cycle 4 with OxMdG and IrMdG.

11.f Surgery

Surgical data will be recorded on the surgery form and returned to UoSCTU within four weeks of the date of surgery. Investigators should make local arrangements to ensure that facilities to snap-freeze samples are available during surgery (if possible). Pathology samples (normal and tumour tissue) obtained following liver resection surgery should be requested and sent to the Cancer Sciences Tissue Bank, Southampton (see section 11c) for those patients who have given consent.

11.g After the end of treatment

After completion of study treatment patients will be followed up with the following tests and procedures every 3 months for 2 years, and every 6 months thereafter until progression for a further 3 years and/or death, using the **Progress report & follow-up form**:

1. Clinical examination.
2. Chest, abdomen and pelvis CT scan (or equivalent imaging). Chest x-ray only to be performed if chest CT not available.
3. A QoL form should also be completed every 3 months for the first year and every 6 months thereafter.
4. Magnesium levels should be measured 6-8 weeks after the last dose of Cetuximab and at intervals until hypomagnesaemia has resolved.
5. Documentation of survival status and further anticancer treatments will be done. All deaths should be reported to UoSCTU using the Death CRF.

Patients who progress whilst in follow-up should come off protocol follow-up but treatment and care outcome data should still be collected. The follow-up only form should be completed at the same study time points.

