- Nail toxicities occur in 8% of patients with Cetuximab, characterised by a paronychia inflammation with associated swelling of the lateral skin folds of toes and fingers, especially great toes and thumbs, which may be painful. It may persist for up to three months after cessation of Cetuximab therapy. Dermatological advice should be sought. Use of daily salt baths and local antiseptic / astringent ointments have been found to be helpful. Anti-inflammatory drugs may help to ease the pain.

Hypomagnesaemia - Cetuximab

- Hypomagnesaemia has been reported in up to 65% of patients following Cetuximab therapy. Patients should have magnesium concentration monitored at baseline, prior to each cycle of chemotherapy and for up to 8 weeks after the last dose of chemotherapy, or until magnesium has normalised, whichever is the longer.
- Fatigue, malaise, tremor, ataxia, carpedal spasm, hyperreflexia, confusion, hallucinations, convulsions and arrhythmias may occur.
- Hypomagnesemia should be corrected by intravenous supplementation if grade 3 (<0.4 mmol/l) or symptomatic. If lesser degrees of hypomagnesemia are detected, oral supplementation may be considered (see Appendix XIII for details).
- Dose modifications for grade 3 toxicity are summarised in the algorithm below. For CTC grade 1 or 2: continue treatment with Cetuximab. If a patient experiences grade 3 toxicity, Cetuximab therapy may be delayed for up to 14 days without changing the dose level. If grade 3 toxicity occurs for a second and third time, Cetuximab therapy may again be delayed for up to 14 days with concomitant dose reductions to 400 mg/m² and then 300 mg/m². Cetuximab dose reductions are permanent. Patients must discontinue Cetuximab if more than 2 consecutive infusions are withheld or grade 3 toxicity occurs for a fourth time despite appropriate dose reduction. If the toxicity resolves to grade 2 or less by the following treatment period, treatment may be resumed.

Dose modifications for Cetuximab-related skin toxicity and hypomagnesaemia:

* These refer to the second and third consecutive week of non-resolving grade 3 toxicity.

Haematological

- Myelotoxicity is similar in frequency as with OxMdG alone. Leucopenia has been reported and attributed to Cetuximab in 8% of patients treated with chemotherapy plus Cetuximab.

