- Check FBC on (or up to 3 working days before) day 1 of each cycle. Delay 1 week if neutrophils $< 1.5 \times 10^9/l$ or platelets $< 75 \times 10^9/l$. Only treat when neutrophils and platelets are above these limits. The lower limit for the day 1 platelet count for this regimen is due to the possible occurrence of mild thrombocytopenia after a number of cycles of OxMdG.
- If >1 delay, or 1 delay of ≥ 2 weeks occurs, maintain Oxaliplatin and infusional 5FU doses but omit bolus 5FU and continue without bolus 5FU for subsequent doses.
- If a further delay(s) for myelotoxicity occurs despite omitting bolus 5FU reduce Oxaliplatin and infusional 5FU doses by 20%.
- Further dose reductions may be made, at the discretion of the treating investigator.

Neurotoxicity

- Oxaliplatin commonly causes peripheral sensory symptoms, easily distinguishable from 5FU neurotoxicity, which is uncommon, and cerebellar.
- Many patients experience transient paraesthesia of hands and feet, and some experience dysaesthesia in the throat. These symptoms are precipitated by cold and last from a few hours to a few days after each Oxaliplatin administration. They do not require treatment or dose reduction.
- If symptoms persist until the next cycle is due, and are associated with significant discomfort or loss of function (e.g. dropping objects), omit Oxaliplatin from the regimen and continue with MdG plus Cetuximab. Infusional 5FU should be increased from $2400\text{mg}/\text{m}^2$ to $2800\text{mg}/\text{m}^2$ during this time (any prior 5FU dose reductions should be taken into account). When symptoms have resolved to grade 1, Oxaliplatin should be restarted at the reduced dose of $75\text{mg}/\text{m}^2$ (infusional 5FU should return to normal).

Renal function (see also Appendix IV)

- Oxaliplatin, like Carboplatin, is not nephrotoxic but is renally cleared.
- Before starting Oxaliplatin, ensure patient fulfils eligibility for renal function (estimated creatinine clearance [Cockcroft] $>50\text{ml}/\text{min}$ or measured GFR [EDTA clearance] $>50\text{ml}/\text{min}$).
- Check serum creatinine at each cycle. If this rises $>25\%$, re-check EDTA clearance or 24-hour urinary clearance, and adjust Oxaliplatin and 5FU doses according to the table in Appendix IV.
- If GFR drops to below $30\text{ml}/\text{min}$, omit Oxaliplatin and reduce 5FU by 25% until recovery.

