- Nail toxicities occur in 8% of patients with Cetuximab, characterised by a paronychia inflammation with associated swelling of the lateral skin folds of toes and fingers, especially great toes and thumbs, which may be painful. It may persist for up to three months after cessation of Cetuximab therapy. Dermatological advice should be sought. Use of daily salt baths and local antiseptic / astringent ointments have been found to be helpful. Anti-inflammatory drugs may help to ease the pain.

Hypomagnesaemia - Cetuximab

- Hypomagnesaemia has been reported in up to 65% of patients following Cetuximab therapy. Patients should have magnesium concentration monitored at baseline, prior to each cycle of chemotherapy and for up to 8 weeks after the last dose of chemotherapy, or until magnesium has normalised, whichever is the longer.
- Fatigue, malaise, tremor, ataxia, carpopedal spasm, hyperreflexia, confusion, hallucinations, convulsions and arrhythmias may occur.
- Hypomagnesemia should be corrected by intravenous supplementation if grade 3 (<0.4 mmol/l) or symptomatic. If lesser degrees of hypomagnesemia are detected, oral supplementation may be considered (see Appendix XIII for details).
- Dose modifications for grade 3 toxicity are summarised in the algorithm below. For CTC grade 1 or 2: continue treatment with Cetuximab. If a patient experiences grade 3 toxicity, Cetuximab therapy may be delayed for up to 14 days without changing the dose level. If grade 3 toxicity occurs for a second and third time, Cetuximab therapy may again be delayed for up to 14 days with concomitant dose reductions to 400 mg/m² and then 300 mg/m². Cetuximab dose reductions are permanent. Patients must discontinue Cetuximab if more than 2 consecutive infusions are withheld or grade 3 toxicity occurs for a fourth time despite appropriate dose reduction. If the toxicity resolves to grade 2 or less by the following treatment period, treatment may be resumed.

Dose modifications for Cetuximab-related skin toxicity and hypomagnesaemia:

* These refer to the second and third consecutive week of non-resolving grade 3 toxicity.

Acute cholinergic syndrome

- Irinotecan may provoke an acute cholinergic syndrome with diarrhoea, sweating, salivation, bradycardia, etc. This may start during the drug infusion or shortly after.
- If this occurs, give atropine sulphate 0.25 mg s/c immediately. Atropine should then be given prophylactically with subsequent cycles.

Haematological

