Appendix XIII – Hypomagnesaemia

Hypomagnesaemia with Cetuximab

Hypomagnesaemia has many well documented causes: predominantly excessive losses through diarrhoea, stoma output or fistula but other causes include renal tubular damage, malnutrition and alcoholism in association with malnutrition, and various drugs. Cisplatin therapy is a well documented iatrogenic cause of renal wasting of magnesium and requires standardized replacement. Other drugs include diuretics, digoxin and prolonged aminoglycoside usage.

There have recently been several reports of hypomagnesaemia and/or hypocalcaemia in relation to Cetuximab therapy, including two abstracts from ASCO GI 2005 (Schrag et. al. 2005 and Carson et. al. 2005). Carson et. al. identified that 65% of patients on single agent Cetuximab developed hypomagnesaemia at a median of 8 weeks of therapy: patients were treated with oral or iv therapy. Despite Oxaliplatin being a platinum derivative, it is not commonly believed to cause symptomatic hypomagnesaemia; however, there may be an enhancing/synergistic effect in combining Oxaliplatin with Cetuximab. The FDA have advised that 'periodic' monitoring for hypomagnesaemia and accompanying hypocalcaemia and hypokalaemia should be undertaken during and for eight weeks after Cetuximab therapy (www.fda.gov/medwatch/safety/200505.htm#Erbix).

Symptoms/Signs

Hypomagnesaemia causes a range of symptoms from non-specific malaise to cardiac arrhythmias and death. However, symptoms of hypomagnesaemia are non-specific and do not always correlate with level of hypomagnesaemia. Hypomagnesaemia may be associated with resistant hypocalcaemia as well as hypokalaemia and hyponatraemia. The magnesium deficit should be corrected in all cases.

Fatigue, malaise, tremor, ataxia, carpopedal spasm, hyperreflexia, confusion, hallucinations, convulsions and arrhythmias may occur. ECG changes include prolonged QT interval and broad flattened T waves. Patients with marked hypomagnesaemia require ECG and intravenous administration of magnesium (see BNF for guide to administration). This may require admission to hospital and should be considered as a SAE/SUSAR to be reported to UoSCTU within 24 hours.

Treatment

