The British National Formulary states that "symptomatic hypomagnesaemia is associated with a deficit of 0.5–1 mmol/kg. Up to 160 mmol Mg²⁺ over up to 5 days may be required to replace the deficit (allowing for urinary losses). Magnesium is given initially by intravenous infusion of magnesium sulphate. Plasma magnesium concentration should be measured to determine the rate and duration of infusion and the dose should be reduced in renal impairment" (BNF 2005).

There appears to be no standard guidelines, with respect to magnesium administration in the well hypomagnesemic patient. Oral supplementation has limitations due to the laxative effect of magnesium salts but lower dose supplementation may be reasonable, "magnesium may be given

by mouth in a dose of 24 mmol Mg²⁺ daily in divided doses; a suitable preparation is magnesium glycerophosphate tablets [not licensed, available from IDIS and Special Products]" (BNF 2005).

Monitoring

It is recommended that magnesium levels are measured:

- at baseline
- prior to each chemotherapy cycle
- for all symptomatic patients
- for any patient with hypocalcaemia

After completion of Cetuximab therapy, magnesium should be measured at 6-8 weeks after the last dose of Cetuximab and at intervals until hypomagnesemia has resolved. This information will be collected on the CRFs and recorded as per NCI CTC toxicity grading criteria (see Appendix XI).

References

Schrag. D, Flombaum.C, Chung.K, Saltz. L; Cetuximab therapy may occasionally cause profound hypomagnesemia and hypocalcemia. Abstract no. 264; ASCO GI 2005

Carson. E, Novak. A, Stella. P; Hypomagnesemia in patients with stage IV colorectal cancer treated with Cetuximab as a single agent; Abstract no. 3655; ASCO GI 2005.

BNF (British National Formulary) March 2005 (Ed)

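### Appendix I times magnesium follow-up from the last chemotherapy dose, whereas Section 11.g and Appendix XIII time it from the last Cetuximab dose

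*Protocol*

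**What the plan says.** The protocol states the magnesium follow-up rule in three places.

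- **Appendix I, Hypomagnesaemia - Cetuximab.** The bullet is the same for OxMdG plus Cetuximab and for IrMdG plus Cetuximab. After a baseline value, magnesium is monitored before each chemotherapy cycle and "for up to 8 weeks after the last dose of chemotherapy, or until magnesium has normalised, whichever is the longer".
- **Section 11.g, After the end of treatment.** "Magnesium levels should be measured 6-8 weeks after the last dose of Cetuximab and at intervals until hypomagnesaemia has resolved".
- **Appendix XIII, Monitoring.** After Cetuximab is complete, "magnesium should be measured at 6-8 weeks after the last dose of Cetuximab and at intervals until hypomagnesemia has resolved". The same appendix cites regulator advice that periodic monitoring "should be undertaken during and for eight weeks after Cetuximab therapy".

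On treatment duration in Arm B, Section 9.b says that "Cetuximab will be continued if chemotherapy is stopped because of toxicity or patient choice". The opposite order is also foreseen. In Appendix I for OxMdG plus Cetuximab, a grade 3 or 4 hypersensitivity reaction ends Cetuximab while the remaining chemotherapy goes on.

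**The concern.** The protocol treats falling magnesium as an effect of Cetuximab. The Introduction describes a progressive decline with the drug. Appendix XIII cites a report of hypomagnesaemia in 65% of patients on Cetuximab alone, at a median of 8 weeks of therapy. A follow-up clock that starts at the last chemotherapy dose therefore starts from the wrong event when Cetuximab outlasts chemotherapy.

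Appendix XIII says that symptoms do not always track the level and that the consequences range up to arrhythmia and death. The grade 3 rules in Appendix I (delay, dose reduction, intravenous replacement) can be applied to a patient without symptoms only if a level has been measured.

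Appendix I is also working text. Section 9.a makes the treating consultant responsible for seeing that Appendices I-IV are followed, and Appendix I suggests copying the relevant schedule into the patient's notes. A site working from that copy alone would see only the chemotherapy anchor.

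**Working it through.** The protocol gives no figure to reproduce here. The check compares the texts and then uses calendar arithmetic to show how far the two anchors can separate.

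**Are the anchors different events?** Section 9.b speaks of chemotherapy stopping while Cetuximab goes on. Appendix I requires an hour between the end of Cetuximab and the start of chemotherapy, and its hypersensitivity rule stops one and continues the other. In these places the two words mean different things, so the last chemotherapy dose and the last Cetuximab dose are different dates.

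**When do they separate?**

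- *Cetuximab outlasts chemotherapy* (Section 9.b): Appendix I gives the shorter follow-up.
- *Chemotherapy outlasts Cetuximab* (Appendix I, hypersensitivity): Appendix I gives the longer follow-up.
- *Only Oxaliplatin is dropped*: Appendix I says to "omit Oxaliplatin from the regimen and continue with MdG plus Cetuximab". MdG is still chemotherapy, so dropping Oxaliplatin does not in itself separate the anchors.
- *Both stop at the same cycle*: the anchors coincide.

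**How far apart can they be when Cetuximab continues alone?**

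Inputs: 14-day cycles (Appendix I); fortnightly Cetuximab (Section 2); 12 weeks of treatment after surgery (Section 9.b), hence 12 / 2 = 6 post-operative cycles, numbered 7 to 12.

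Assumptions for illustration: all chemotherapy stops after cycle k, and Cetuximab alone continues to the planned infusion 12.

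Set the last Cetuximab dose (cycle 12) at week 0. Cycle k then falls at week -2 x (12 - k). The 8-week limit in Appendix I falls at week 8 - 2 x (12 - k). With a Cetuximab anchor it falls at week 8 in every row.

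| Chemotherapy stops after cycle k | Cetuximab-only infusions | Last chemotherapy (week) | Appendix I limit (week) | Shortfall (weeks) |
|---|---|---|---|---|
| 11 | 1 | -2 | +6 | 2 |
| 10 | 2 | -4 | +4 | 4 |
| 9 | 3 | -6 | +2 | 6 |
| 8 | 4 | -8 | 0 | 8 |
| 7 | 5 | -10 | -2 | 10 |

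Only in the last row does the limit fall before the final Cetuximab dose. None of these rows depends on the length of the surgical break.

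The normalisation clause lengthens the period for a patient whose magnesium is low when the limit is reached. It does nothing for a patient whose level is still normal then and falls later.

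**The reverse order.** If Cetuximab stops after cycle k and chemotherapy runs to cycle 12, the Appendix I limit is 8 + 2 x (12 - k) weeks after the last Cetuximab dose: 10 weeks for k = 11 and 18 weeks for k = 7. A Cetuximab anchor gives 8 weeks in both cases.

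**The case against.** The strongest reply is that the rules add up. Nothing in Appendix I cancels the test in Section 11.g, which is main-body text, or the one in Appendix XIII. A site can meet all three by testing up to the later date. This largely stands, and it is why the point is minor. A reader might infer that patients go untested after Cetuximab or that hypomagnesaemia will be missed. The documents do not support that, because a test 6-8 weeks after the last Cetuximab dose is called for in two other places.

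A second reply is that chemotherapy can be read to include Cetuximab. The Section 3 schedule has a row beginning "Chemotherapy - Cetuximab (if applic". Appendix I lists the Cetuximab combinations among its chemotherapy regimens, and Section 11.e records Cetuximab administration under the chemotherapy cycle. Usage is therefore mixed. But Section 9.b and the dosing text of Appendix I itself separate the two, so this reading does not reconcile the bullet with Section 11.g.

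Two further readings are tempting.

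- *Cetuximab given alone would have no pre-dose magnesium test.* No sentence says whether such a visit counts as a cycle, but Section 11.e and the Arm B scheduled tests lean towards including it. This is unclear drafting and is not raised as a separate fault.
- *The Section 3 footnote limits magnesium testing to symptomatic patients.* It contains no word of restriction and matches the symptom trigger that Section 9.a and Appendix XIII list beside testing before every cycle. The layout of that table cannot be judged from the extracted text.

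**Conclusion.** The inconsistency is real. Two bullets in Appendix I use an anchor that conflicts with Section 11.g, with Appendix XIII and with the regulator advice that Appendix XIII cites. The anchors separate in both directions. The direction that matters for safety is Cetuximab continuing alone, where the Appendix I period is short by two weeks for each Cetuximab-only infusion: 2 to 10 weeks in the illustration.

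Those figures assume 14-day cycles, a complete stop of chemotherapy after surgery, and Cetuximab given as planned to infusion 12. They show how far the wordings can differ. They are not an expected effect, because the protocol does not say how many patients continue on Cetuximab alone.

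The point is a minor correction of safety wording that should be made. It has no bearing on the primary endpoint, the sample size or the primary analysis.

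**What to change.** In both Appendix I bullets (OxMdG plus Cetuximab and IrMdG plus Cetuximab), replace "prior to each cycle of chemotherapy and for up to 8 weeks after the last dose of chemotherapy" with wording to this effect: before each cycle, including Cetuximab given alone, and until 8 weeks after the last dose of Cetuximab. Keep the clause that extends monitoring until magnesium is normal, whichever is longer. State that pre-cycle testing continues while any trial chemotherapy is being given.

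The change has two costs:

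- **Extra tests.** At most one added magnesium measurement per Cetuximab-only visit, so up to five for one patient in the illustration. It adds none if such visits are already handled as cycles.
- **A shorter tail in the reverse case.** When chemotherapy outlasts Cetuximab, Appendix I follow-up would end 8 weeks after Cetuximab instead of 8 weeks after chemotherapy. Pre-cycle testing during the remaining chemotherapy and the normalisation clause soften this. If the trial team wants to keep the longer tail, the bullet can count from the later of the two last doses.
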